b Fitusiran as prophylaxis treatment and permitted on-demand use of factors or BPAs for treatment of breakthrough bleeding episodes. Patients may continue their routine factor or BPA administration schedule for up to the first 7 days of the onset period. For the United States specific requirements see [Section 11.6.1.1](#).

c Not required at Early Termination Visit for patients who complete assessment at EOT Visit and subsequently Early Terminate.

- d* Patients who discontinue study drug dosing for any reason and agree to complete the remaining assessments through the EOS/ET and AT FU visits and may receive treatment consistent with local standard practice for their disease per Investigator judgement, as applicable. For patients who withdraw from the study early and do not consent to complete remaining assessments through the EOS/ET and AT FU visits, every effort should be made to conduct the assessments performed at the EOS/ET visit.
- e* Patients not enrolling in the extension study will complete AT F/U visits at monthly intervals following final fitusiran dose until AT activity level returns to ~60% (per the central laboratory), or per Investigator discretion in consultation with the study Medical Monitor.
- f* The complete medical history/disease history (ie, including bleeding episode and treatment history over the prior 6 months) to be recorded at Screening.
- g* eDiary training will be completed at the Clinic at Screening (see [Section 7.2.1](#)).
- h* A full physical examination will be performed at Screening only; a directed physical exam will be performed at all other visits (see [Section 7.6.3](#)).
- i* Height will be recorded only at Screening for patients > 18 years old. Height for patients < 18 years old and weight for all patients will be recorded at all checked visits ([Section 7.6.2](#)).
- j* 12-lead ECGs will be performed in triplicate. On Day 1, 12-lead ECGs will be performed predose and 4 hours (± 30 min) postdose (see [Section 7.6.4](#)). The Month 7 12-lead ECG will be performed only in those patients who are performing the ET visit and may be performed in singlicate.
- k* Hepatitis C virus antibody positive patients only. FibroScan where available, otherwise FibroTest and APRI.

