1.5 BENEFIT-RISK ASSESSMENT

Based on the available clinical data (see [Section 1.2.2](#)), fitusiran may be able to offer potentially reduced bleeding rates for patients receiving factor concentrate or BPA treatment prophylactically or on-demand. Further, the pharmacodynamic profile of fitusiran results in consistent reduction of AT and therefore may provide more consistent increase in thrombin generation and hemostatic protection throughout the dosing interval. The clinical experience to

date suggests that in hemophilia A or B patients, with or without inhibitors, fitusiran treatment is associated with reductions in AT, increases in thrombin generation, and reduction of the number of bleeding episodes.

Identified risks of fitusiran include serious vascular thrombosis, liver transaminase abnormalities, cholecystitis, and symptomatic cholelithiasis. In addition, serious hypersensitivity reactions, including injection site reactions, are considered a potential risk of fitusiran. The risk of vascular thrombotic events is thought to be elevated in patients receiving fitusiran with AT activity levels <10%. In addition, the concomitant treatment of breakthrough bleeding episodes with factor or BPA, due to particularly at doses higher than recommended in the protocol may confer an increased risk of thrombotic events. Additional details regarding the benefits and risks of fitusiran are provided in the Investigator's Brochure.

This clinical protocol has exclusion criteria intended to minimize the risk of thrombosis, liver transaminase abnormalities, and serious ISRs. With respect to the risk of thrombosis, the protocol includes a change in the fitusiran dosing regimen to minimize the occurrence of AT levels <10% ([Section 6.2.3.2](#)), detailed guidance and oversight on treatment of breakthrough bleeding episodes with reduced factor and/or BPA dosing ([Section 6.3.2](#)), and monitoring and management of thrombosis while patients are on fitusiran ([Section 6.5](#)). The protocol also excludes patients with evidence of liver disease (including active viral hepatitis) and stipulates ongoing monitoring for elevated transaminases ([Section 6.2.3.1](#)). The safety of trial patients will be overseen by an independent DMC ([Section 4.7](#)).

For the United States specific requirements, see [Section 11.6.1.2](#).

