5.3.1 Discontinuation of study drug

The Investigator or designee may discontinue dosing in a patient if the patient:

- Is in significant violation of the protocol
- Is non-adherent to treatment regimen
- Experiences a serious or intolerable AE, a life-threatening bleeding episode, eg, any gastrointestinal hemorrhage or intracranial hemorrhage, or life-threatening thromboembolic event
- Requires a prohibited medication
- More than 1 AT measurement <15% if at a dose of 50 mg Q2M

The Investigator will confer with the Sponsor or study Medical Monitor before discontinuing dosing in the patient.

Patients (or their guardians) may decide to discontinue study drug.

In general, patients who discontinue study drug dosing for any reason will be encouraged to remain on the study to complete the remaining assessments through the end of study so that their experiences are captured in the final analyses. If a patient discontinues dosing due to a serious adverse event (SAE), the SAE should be followed as described in [Section 7.6.6](#). When a patient discontinues study drug dosing, the primary reason must be recorded in the appropriate section of the eCRF. Patients who discontinue study drug but who remain on study may receive treatment consistent with local standard practice for their disease per Investigator judgement, as applicable. Safety will be captured for the entire duration of study for patients who discontinue treatment.

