| | Factor VIII | Factor IX Standard half- life | Factor IX Extended half- life | aPCC | Recombinant Factor VIIa |
|--------------------------------------|--|-------------------------------------|-------------------------------------|--|----------------------------|
| Recommended single dose of | 10 IU/kg | 20 IU/kg | 20 IU/kg | 30 U/kg | ≤45 µg/kg |
| Single Dose should not exceed | 20 IU/kg | 30 IU/kg | 30 IU/kg | 50 U/kg | 45 µg/kg |
| Repeat dose instructions | Mandatory to call the clinical study center prior to second dose Consider evaluation and treatment at the clinical study center (see Section 6.4) | | | Mandatory to call site prior to third dose | |

| Should not repeat in less than 24 hours | Should not repeat in less than 24 hours | Should not repeat in less than 5-7 days | Should not repeat in less than 24 hours | Should not repeat in less than 2 hours |
|--|---|---|---|---|
| Should be seen at site within 48-72 hours if more than 2 doses are required (see Schedule of Assessments Table 1 for assessments) | | | | Should be seen at site within 48-72 hours if more than 3 doses are required |
| For situations requiring higher doses, more frequent administration, multiple repeated doses, discussion with study Medical Monitor and Clinical Advisor is recommended, and AT replacement should be considered. | | | | |
| Do not use antifibrinolytics in combination with factor or BPA. | | | | |

Note: Adjunctive management of bleeding episodes should be carried out per standard of care. For the United States specific requirements, see [Section 11.6.1.2](#). For the Japan specific requirements, see [Section 11.6.2](#).

6.3.2.3 Use of factor or bypassing agents following discontinuation of fitusiran (for the United States specific requirements, see Appendix 11.5.1.2)

Resuming routine prophylaxis following discontinuation of fitusiran

Patients who opt to discontinue fitusiran may resume standard prophylaxis with factor concentrates or BPAs when their AT activity level returns to approximately 60% (per the central laboratory). An earlier restart of standard treatment may be considered in conjunction with consultation from the study Medical Monitor, if a strong medical need arises (eg, increased frequency of bleeding).

Bleed episode management following discontinuation of fitusiran

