Patients who opt to discontinue fitusiran may resume standard on-demand dosing with factor concentrates or BPAs for bleeding episodes when their AT residual activity level returns to approximately 60% (per the central laboratory). An earlier restart of standard treatment may be considered in conjunction with consultation from the study Medical Monitor, if a strong medical need arises (eg, increased frequency of bleeding). If full doses of factor or BPA are required to achieve hemostasis prior to AT recovery (approximately 60% residual activity per the central laboratory), AT replacement should be considered.

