| Recommended single dose of | 10 IU/kg | 20 IU/kg | 20 IU/kg | 30 U/kg | ≤45 µg/kg |
| Single Dose should not exceed | 20 IU/kg | 30 IU/kg | 30 IU/kg | 50 U/kg | 45 µg/kg |
| Repeat dose instructions | Mandatory to call the clinical study center prior to second dose Consider evaluation and treatment at the clinical study center (see Section 6.4) | | | | Mandatory to call site prior to third dose |
| | Should not repeat in less than 24 hours | Should not repeat in less than 24 hours | Should not repeat in less than 5-7 days | Should not repeat in less than 24 hours | Should not repeat in less than 2 hours |
| | Should be seen at site within 48-72 hours if more than 2 doses are required (see Schedule of Assessments Table 1 for assessments) | | | | Should be seen at site within 48-72 hours if more than 3 doses are required |

For situations requiring higher doses, more frequent administration, multiple repeated doses, discussion with study Medical Monitor and Clinical Advisor is recommended, and AT replacement should be considered.

Do not use antifibrinolytics in combination with factor or BPA.

Note: Doses of FVIII and FIX are included for completeness. It is expected that these non-inhibitor patients will be managed with factor concentrates and inhibitor patients will be routinely managed with rFVIIa or aPCC for bleeding episodes. Adjunctive management of bleeding episodes should be carried out per standard of care.

Section 6.3.2.3 Use of ~~Factor or~~ Bypassing agents following discontinuation of fitusiran

Resuming routine prophylaxis following discontinuation of fitusiran

Patients who opt to discontinue fitusiran may resume standard prophylaxis with ~~factor concentrates or~~ B-PAs when their AT activity level returns to approximately 60% (per the central laboratory). An earlier restart of standard treatment may be considered in conjunction with consultation from the study Medical Monitor, if a strong medical need arises (eg, increased frequency of bleeding).

Bleed episode management following discontinuation of fitusiran

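### Section 5.3.1 and Table 1 footnote d set no antithrombin condition for returning to local standard treatment after fitusiran, while Section 6.3.2.3 sets one of about 60% but words it only for patients who opt to stop

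*Protocol*

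**What the plan says.** **Open permission.** After listing reasons for stopping dosing, one of which is more than one AT value below 15% on 50 mg Q2M, Section 5.3.1 says: "Patients who discontinue study drug but who remain on study may receive treatment consistent with local standard practice for their disease per Investigator judgement". Table 1 footnote d has the scope "Patients who discontinue study drug dosing for any reason and agree to complete the remaining assessments" and the same content: such patients "may receive treatment consistent with local standard practice for their disease per Investigator judgement, as applicable". Neither text gives an AT level or a waiting time, and neither points to Section 6.3.2.3.

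**Conditional permission.** Section 6.3.2.3 has one sentence for prophylaxis, "Patients who opt to discontinue fitusiran may resume standard prophylaxis with factor concentrates or BPAs when their AT activity level returns to approximately 60" per cent, and a parallel one for bleeds, "Patients who opt to discontinue fitusiran may resume standard on-demand dosing with factor concentrates or BPAs for bleeding episodes", on the same AT condition. It has one exception, for a pressing clinical reason: "An earlier restart of standard treatment may be considered in conjunction with consultation from the study Medical Monitor". The US version in Section 11.6.1.2 keeps the same subject: "Patients who opt to discontinue fitusiran may resume standard prophylaxis with" BPAs, on the same AT condition.

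**Stops that are not a choice.** Section 6.2.3.2 makes permanent discontinuation compulsory after more than one AT level below 15% on 50 mg Q2M. Section 6.2.3.1 and Table 4 do so for defined transaminase findings.

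**Stated risk.** On factor or BPA given for breakthrough bleeds under fitusiran, Section 1.5 says that this treatment, "particularly at doses higher than recommended in the protocol may confer an increased risk of thrombotic events".

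**The concern.** Two sets of passages govern the same decision, namely when a patient who has stopped fitusiran goes back to ordinary factor or BPA treatment. One leaves it to Investigator judgement. The other attaches an AT threshold or a Medical Monitor consultation.

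The wording of the second set also leaves a gap. Section 5.3.1 itself distinguishes the Investigator stopping dosing from the patient or guardian deciding to stop, and 'opt' fits only the latter. Patients taken off drug because their AT was too low are therefore the ones whom the AT-recovery sentences do not literally reach.

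What is at stake is mainly safety. The protocol caps bleed-treatment doses under lowered AT because of thrombosis, and a site following Section 5.3.1 alone could bypass that scheme without departing from the text. There is also a smaller cost for interpretation. The SAP (Section 2.1.4) runs the treatment-emergent period to the end of the study, so a thrombosis after stopping counts as treatment-emergent whichever passage the site followed.

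**Working it through.** The point is one of wording, and the plan states no figure to reproduce. The passages are set side by side first, and Table 3 is then used to see how often the 60% condition would matter.

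**1. Conditions attached to standard treatment after stopping**

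| Passage | Who | AT condition | Consultation on restart |
|---|---|---|---|
| Section 5.3.1 | Discontinuers remaining on study | None | None |
| Table 1 footnote d | Discontinuers for any reason who complete assessments | None | None |
| Section 6.3.2.3 and US copy | Those who opt to stop | About 60% | Needed only for earlier restart |

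The consultation that Section 5.3.1 does require concerns the decision to stop fitusiran, not the return to standard doses.

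**2. The two readings of 'opt'**

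- Narrow: patients stopped under Section 6.2.3.2 or the liver rules did not opt. They have the open permission and are outside the 60% sentences. This is a gap.
- Broad: 'opt' means anyone who stops. Section 5.3.1 and footnote d then permit without condition what Section 6.3.2.3 permits conditionally, for every discontinuer on study. This is a conflict.

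Neither reading leaves the text consistent.

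**3. Other protections**

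- Section 6.3.2.3 asks sites to consider AT replacement if full doses are needed for hemostasis before recovery. This is not limited to those who opt, but it is advisory and does not address restarting prophylaxis.
- Sections 6.3.1.2 and 6.3.2.2 limit factor/BPA after Day 7 of the fitusiran treatment period to bleeds and procedures. They do not say expressly that this continues after dosing stops. If it does, it is a further text at odds with Section 5.3.1.

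**4. How often 60% would bind (Protocol Table 3, 50 mg Q2M, steady state, 1000 virtual patients)**

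- Peak AT, 5th / median / 95th percentile: 17.87 / 32.37 / 56.42. Since 56.42 < 60, at least 95% of simulated patients are below 60% even at their highest point in the interval. The simulated maximum is 77.5, so a few exceed it.
- Trough AT: 13.9 / 23.3 / 39.7. Since 13.9 < 15, at least 5% have a trough below 15%, so the group that the AT rule addresses is not empty.

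As a side check, assume a lognormal shape with s = ln(P50/P5)/1.645 or s = ln(P95/P50)/1.645, and P(AT < c) = Φ(ln(c/P50)/s).

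- Peak: s = 0.361 or 0.338. P(AT < 60) = Φ(0.617/0.361) = 0.956, or Φ(0.617/0.338) = 0.966.
- Trough: s = 0.314 or 0.324. P(AT < 15) = Φ(−0.440/0.314) = 0.080, or Φ(−0.440/0.324) = 0.087.

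The trough figure is the share with a trough below 15%, not the share stopped, because the rule needs more than one such value.

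**The case against.** The best defence is that a general and a specific provision can be read together. The title and subheadings of Section 6.3.2.3 speak of discontinuation without limiting the reason, so 'opt' may be loose drafting. Section 5.3.1 defers to Investigator judgement and does not mention doses or regimens. That is a fair account of what was probably meant. It does not settle the matter, because the operative sentences and the US copy all use 'opt', and nothing in Section 5.3.1 or footnote d sends the reader to Section 6.3.2.3.

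Other parts of the defence stand and limit the point. Several stronger inferences are not supported:

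- *Patients may restart their full regimen immediately.* The passages give no timing. They lack an AT or time condition, which is not the same as permitting immediate restart.
- *The two rules clash for months after stopping.* Neither document gives AT recovery times after a stop at a low level. Table 3 describes steady state under continued dosing.
- *Thrombosis is another compulsory stop left unprotected.* Section 5.3.1 only allows stopping for a life-threatening event, and Section 6.5 gives thrombosis its own guidance.
- *Completers who do not enter the extension are caught too.* The open permission concerns patients who discontinue study drug, so completers gain no competing permission from it.
- *Low-AT patients lose every safeguard.* They fall outside the 60% sentences only. The partial protections above may still apply.
- *The efficacy result is compromised.* The primary on-treatment analysis excludes bleeds from 29 days after the last dose, or 57 days on Q2M (SAP Section 2.1.3.1), and no effect on any analysis can be quantified from the documents.

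**Conclusion.** The inconsistency is real and needs correcting. Section 5.3.1 and footnote d carry no AT condition. Section 6.3.2.3 carries one but words it for patients who opt to stop. The result is a gap for rule-stopped patients or a conflict for all discontinuers on study, depending on how that word is read.

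If applied, the 60% condition would bind at least 95% of patients stopping around a due dose at steady state on 50 mg Q2M. That rests on the protocol's own simulation. It does not extend to patients stopping after a first dose, or to 80 mg monthly, which has no row in Table 3. The 8.0% to 8.7% for a trough below 15% rests on the lognormal assumption as well.

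The number affected in this study is likely to be small. The AT stopping rule exists only for 50 mg Q2M, and SAP Section 2.4 reports 2 participants on that regimen. The liver stops and voluntary stops are not confined to it. The case for correction rests on the safeguard involved and the low cost, not on numbers. No view is taken on which restart condition is clinically right.

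**What to change.** Reconcile Section 5.3.1, Table 1 footnote d, Section 6.2.3.2, Section 6.3.2.3 and the US copy in Section 11.6.1.2 so that a single rule:

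- states which discontinuing patients the AT condition covers, naming those who stop by choice and those stopped by the AT or liver rules;
- says whether the post-Day 7 limits in Sections 6.3.1.2 and 6.3.2.2 continue after dosing stops;
- is consistent with Section 6.5 for thrombosis cases.

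Section 5.3.1 and footnote d should cross-refer to that rule. The heading of Section 6.3.2.3 also sends US sites to Appendix 11.5.1.2, although the US text is in Section 11.6.1.2, and this can be corrected at the same time. Which restart condition applies, and to whom, is for the sponsor's clinical team and the DMC.

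The cost is a few sentences in an amendment or a clarification letter to sites. No visits, tests or analyses are added.

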5.3.2 Withdrawal from study

A patient or guardian may withdraw consent from study participation at any time. The Investigator may withdraw a patient at any time if this is considered to be in the patient's best interest. Any withdrawal from the study must be fully documented in the eCRF and should be followed-up by the Investigator.

However, study integrity and interpretation is best maintained if all enrolled patients continue study assessments and follow-up even if study treatment is discontinued. Patients considering withdrawing from the study should be informed that they can discontinue treatment and still remain in the study to complete study assessments and follow-up as specified in the Schedule of Assessments ([Table 1](#)). If a patient still chooses to discontinue study treatment and withdraw from all follow-up, every effort should be made to conduct the EOS/ET assessments within 4 weeks of the last dose (see [Table 1](#)). When a patient withdraws from the study, the withdrawal of consent and the reason for withdrawal must be recorded in the appropriate section of the eCRF and all efforts will be made to complete and report the observations as thoroughly as possible. There will be no replacements of patients who withdraw from this study.

5.3.3 Criteria for temporarily delaying enrollment or administrations of study intervention

During a regional or national emergency declared by a governmental agency, if the site is unable to adequately follow protocol mandated procedures, contingency measures are proposed in [Section 11.8](#) for screening, enrollment and/or administration of study intervention.

6 TREATMENTS

6.1 TREATMENTS ADMINISTERED

Study drug supplied for this study must not be used for any purpose other than the present study and must not be administered to any person not enrolled in the study. Study drug that has been dispensed to a patient and returned unused must not be re-dispensed to a different patient.

The IMP may be supplied at the site or from the Investigator/site/Sponsor to the patient via a Sponsor-approved courier company where allowed by local regulations and agreed upon by the patient.

For a regional or national emergency declared by a governmental agency that results in travel restrictions, confinement, or restricted site access, contingency measures are included in [Section 11.8](#).

6.2 INVESTIGATIONAL MEDICINAL PRODUCT

Detailed information describing the preparation, administration, and storage of fitusiran is provided in the Pharmacy Manual.

6.2.1 Description

Fitusiran (SAR439774) solution for injection (SC use) will be supplied as a sterile solution (see Pharmacy Manual for further details of solution concentration and fill volume).

6.2.2 Dose and administration

Patients will receive open-label fitusiran as an SC injection, during the fitusiran treatment period for a total of 7 months; dosing will begin on Day 1 of the fitusiran treatment period ([Table 1](#)).

Study drug injection will be administered at the clinic by qualified staff under the supervision of the Investigator or designee. Detailed instructions for study drug administration are found in the Pharmacy Manual.

Study drug will not be blinded as this is an open-label study. See [Section 6.2.5](#) regarding packaging and labeling.

If a patient does not receive a fitusiran dose within the specified dosing window ([Table 1](#)), the Investigator should contact the study Medical Monitor. After such consultation, the dose may be administered or considered missed and not administered.

If a patient misses a dose, the Investigator, in consultation with the study Medical Monitor, will discuss whether the patient will be able to continue on the study.

Additional details regarding dosing can be found in the Pharmacy Manual.

